Physical Activity Intervention for Adolescent Girls

Clinical Trials NCT04190225

Study Protocol and Statistical Analysis Plan

September 4, 2024

Trial Design and Setting

Chicas Fuertes is a parallel group randomized trial. Adolescent Latinas (N=200) living in San Diego County are randomized 1:1 to receive either the mobile technology-based MVPA intervention or only a wearable tracker (control group); analyses will test the superiority of the intervention over the control condition in increasing MVPA. Participants assigned to the intervention first receive a face-to-face counseling session to learn behavior change techniques. These sessions are conducted in a number of settings such as local parks, classrooms, and community-based organizations. They then receive a Fitbit and access to a tailored intervention website to reinforce goal setting and self-monitoring. Participants also are connected to a study Instagram account, and receive regular text messages automatically generated by data from wearable trackers that update participants on goal progress and encourage adaptive goal setting. Activity is measured at baseline and follow-up via accelerometers and the 7-Day Physical Activity Recall (PAR) Interview, and throughout the study using Fitbits. Measures are taken again at 12 months to evaluate maintenance of activity gains. The sponsor and funder, the National Institutes of Health, played no part in study design. They have no role in the collection, management, analysis, and interpretation of data. They played no part in writing of the protocol and the decision to submit the protocol for publication. The study protocol uses SPIRIT reporting guidelines ¹.

Participants

Eligibility criteria

Potential participants must self-identify as Latina, be 13-18 years old, read, write, and speak English, and be underactive, defined as regularly participating in MVPA for less than 150 minutes per week. Participants must also have regular (≥ 2 times/week) access to the Internet and to a cell phone that can receive and send text messages. Interested participants who do not have access to a smartphone are provided equipment to sync the Fitbit with a computer and

use the Fitbit website dashboard rather than the smartphone app.

Intervention

Intervention description

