To increase enrollment and retention in the study, Fitbit devices and incentives in the form of cash payments and gift cards are provided to all participants. At baseline, each participant receives a Fitbit Inspire HR activity tracker to use throughout the study and keep after study participation is completed. Incentive payments of \$25, \$50, and \$50 are provided at the baseline, 6-, and 12-month follow-up measurement visits, respectively. Additionally, participants receive an additional \$25 bonus if they complete all measures at the 6- and 12-month visits. Lastly, while in-person research was suspended at UC San Diego (March 2020 – August 2020) and is limited (August 2020 – present) to mitigate the spread of COVID-19, remote follow-up measurement visits are offered to participants unable to return in-person. This includes completing self-report surveys online.

Outcomes

Primary outcome

The primary outcome is change in weekly minutes of MVPA from baseline to six months measured by the ActiGraph GT3X+ accelerometer. The ActiGraph GT3X+ is a hip-worn triaxial accelerometer which measures movement and intensity of activity and has been validated against heart rate telemetry ⁹ and total energy expenditure ¹⁰, including in children.¹¹ Participants wear the ActiGraph for ≥ 12 hrs/day ≥ 7 days at baseline and follow-up. Participants receive regular text messages to remind them to wear the ActiGraph. Valid wear time is considered ≥ 3000 minutes on ≥ 4 days. Data is processed using Freedson's age-specific cut points for children to identify activity at various intensities.¹² We will evaluate total minutes of MVPA and total time in 10+ minute bouts.

As an additional measure of MVPA change, at baseline and follow-up participants also engage in the 7-Day PAR interview. The 7-Day PAR is a semi-structured interview that assesses frequency, duration and intensity of MVPA. It has consistently demonstrated acceptable reliability, internal consistency, and congruent validity with objective MVPA measures ^{13,14} and sensitivity to changes over time.^{15,16} It has been validated in children as young as 11.¹⁷ Administering the PAR requires annual certification. To ensure fidelity of PAR measures, a random sample of 5% of PAR interviews are recorded and assessed for fidelity by an external consultant.

Secondary outcomes and covariates

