At 12 months, participants in the intervention group were asked to complete a consumer satisfaction measure to assess the acceptability of the intervention. This is modified from our previous studies.

Screening and consenting

Potential participants may contact research staff through Instagram direct message, Facebook, email, or text/call via the study phone number. Interested participants are then called to participate in the telephone screener that includes a description of the study purpose, procedures, risks, benefits, and eligibility requirements. If participant is under the age of 18, research staff first talk with her parent/guardian before screening her to ask basic eligibility questions and to receive parental consent to screen the daughter, then speak to the adolescent to complete screening. If eligible, interested participants are invited to engage in an orientation session via Zoom.

Orientation visit

Prior to the orientation session, participants are instructed to download the Fitbit app and set up an account. They are also provided with an orientation packet via mail, including a Fitbit Inspire HR, a hip-worn accelerometer, and an orientation folder that includes a consent form, assent form, instructions on how to use the Fitbit, and instructions for wearing the accelerometer. The girl's parent/guardian is invited to attend the first half of the orientation via Zoom to review a PowerPoint presentation that outlines the procedures, benefits, and expectations of the study. Following the presentations, the participant and their parent/guardian sign the written informed consent and assent forms, which are collected the following week at the baseline visit. The second half of the orientation is used to set up the Fitbit, including syncing it with a smartphone, connecting it to the study's online Fitabase database, and temporarily blinding the Fitbit monitor and app to prevent feedback from influencing baseline activity. We also review the Fitbit and accelerometer expectations, and schedule the Baseline visit for 7 days after the orientation.

Over the next week, participants wear the Fitbit wrist monitor, and a hip worn GT3X+ accelerometer, with instructions to wear it 12 hours per day for seven days. Before the baseline visit, they also fill out online psychosocial measures, including self-efficacy, stage of change for activity, and social support (see Measures).

Baseline visit

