As min/week of MVPA was skewed and attempts to transform towards normality were unsuccessful, a series of quantile regression models with bootstrapped standard errors (10,000 bootstrapped samples) were used to regress median min/week MVPA on baseline values, group, and covariates. Models were run separately for self-reported MVPA (via the PAR) and objectively measured (using accelerometry). Models for the latter further adjusted for accelerometer wear time. As a small proportion of study participants were yoked together during the randomization process (siblings, cousins, or close friends who enrolled together), we adjusted for clustering by yoked group in each of our models (to ensure standard errors were adjusting for non-independence of outcomes within-cluster). All other covariates were balanced at baseline and tested for significance in the model before being dropped.

To understand the group differences in minutes of PA as collected via the Fitbit, we examined data from the weeks corresponding to measurement of PA via the PAR and accelerometer. Using a longitudinal mixed effects model with subject-specific intercepts, we examined group differences adjusting for clustering by yoked pair.

All analyses were carried out in R, with significance level set at .05 a priori.

1. Chan A-W, Tetzlaff JM, Gøtzsche PC, et al. SPIRIT 2013 explanation and elaboration: guidance for protocols of clinical trials. *BMJ : British Medical Journal*. 2013;346:e7586. doi:10.1136/bmj.e7586

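### The Fitbit model names no visit term, group-by-visit term or baseline adjustment although its weeks appear to include the pre-randomisation week, so the effect is either diluted or estimated less precisely than the data allow

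*Combined protocol and SAP*

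**What the plan says.** The Fitbit paragraph of the STATISTICAL ANALYSIS section defines the data and the model in two sentences. On the data: "we examined data from the weeks corresponding to measurement of PA via the PAR and accelerometer". On the model: "Using a longitudinal mixed effects model with subject-specific intercepts, we examined group differences adjusting for clustering by yoked pair". It lists no fixed effects other than group, and it does not say which coefficient is the result.

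Other sections show which weeks these are. Under Primary outcome, "at baseline and follow-up participants also engage in the 7-Day PAR interview", and the accelerometer follows the same pattern. Follow-up visits puts the later measurements at 6 and 12 months. Under Orientation visit, the Fitbit is worn in the week before the baseline visit, after staff have set it up by "temporarily blinding the Fitbit monitor and app to prevent feedback from influencing baseline activity". Baseline visit places randomisation after all baseline measures are complete, and the randomisation section says that the trackers are unblinded only after allocation.

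The paragraph before the Fitbit one is more explicit. The PAR and accelerometer models "regress median min/week MVPA on baseline values, group, and covariates".

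**The concern.** On a plain reading, one of the three Fitbit weeks precedes randomisation. The expected arm difference in that week is zero by design. A group term that spans all three weeks is therefore an average of two post-randomisation differences and a zero. The PAR and accelerometer models do not have this problem, because baseline enters them as a covariate.

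Fitbit activity is listed among the secondary outcomes, and its result will be read next to those from the ActiGraph and the PAR. A diluted Fitbit estimate could be taken as a failure to replicate when the underlying effect is the same. The target coefficient is also left open. A pooled term, a 6-month contrast and a 12-month contrast can give different answers, and nothing in the plan fixes the choice ahead of the data.

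**Working it through.** The documents give no Fitbit power, SD, correlation, effect size or dropout, so there is no planned figure to reproduce. Everything below is conditional.

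**Inputs from the documents**
- Sample size: "Adolescent Latinas (N=200) living in San Diego County are randomized 1:1", taken as n = 100 per arm.
- Alpha: "significance level set at .05 a priori", taken as two-sided because the sidedness is not stated.
- Weeks: baseline, 6 and 12 months.

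**Assumptions**
- Standardised effect d, equal at 6 and 12 months unless stated otherwise.
- Equal variance (set to 1) and a common correlation rho between weeks.
- Complete data unless stated otherwise; yoking ignored.

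**Step 1: what a pooled group term estimates.** The expected coefficient is (0 + d + d)/3 = 2d/3, whatever rho is. Generalised least squares with a random-intercept covariance gives 0.667d both without and with visit main effects, so a visit main effect alone does not remove the dilution. Departures from the simple case:
- If the 12-month effect is half the 6-month effect: (0 + 1 + 0.5)/3 = 0.50 of the 6-month effect.
- If the effect is gone by 12 months: 1/3 of the 6-month effect.
- If 10% of 6-month and 20% of 12-month weeks are missing, at random and alike in both arms: 0.61 to 0.62 of d for rho from 0.3 to 0.7. With 20% and 30% missing: 0.57 to 0.59 of d.

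**Step 2: effect averaged over both follow-ups.** The SE of each contrast is sqrt(2v/n), and power is approximately Φ(effect/SE − 1.96).
- Pooled group term: effect 2d/3, v = (1 + 2rho)/3.
- Group-by-post contrast, baseline left free: effect d, v = (1 + rho)/2 + 1 − 2rho.
- Follow-up mean with baseline as covariate: effect d, v = (1 + rho)/2 − rho².

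At rho = 0.5 and d = 0.4:
- Pooled: v = 0.667, SE = 0.115, effect 0.267, ratio 2.31, power 64%.
- Group-by-post: v = 0.75, SE = 0.122, ratio 3.27, power 90%.
- Baseline-adjusted: v = 0.50, SE = 0.100, ratio 4.00, power 98%.

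| d | rho | Pooled | Group-by-post | Baseline-adjusted |
|---|---|---|---|---|
| 0.3 | 0.3 | 49% | 54% | 81% |
| 0.3 | 0.5 | 41% | 69% | 85% |
| 0.3 | 0.7 | 35% | 89% | 94% |
| 0.4 | 0.3 | 73% | 79% | 97% |
| 0.4 | 0.5 | 64% | 90% | 98% |
| 0.4 | 0.7 | 56% | 99% | 99.7% |

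**Step 3: the 6-month contrast alone, with no dilution.** With a group-by-visit term and a free baseline, the contrast against baseline has v = 2(1 − rho). With baseline adjustment, v = 1 − rho². The ratio is 2(1 − rho)/(1 − rho²) = 2/(1 + rho), which is 1.54 at rho = 0.3, 1.33 at 0.5 and 1.18 at 0.7. At rho = 0.5 and d = 0.4, power is 81% against 90%.

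**The case against.** The strongest reply is that the text does not show pooling. It names no time or baseline terms, but it excludes none either. The model is called longitudinal, and the section Secondary outcomes and covariates frames the Fitbit aim as a comparison of how activity trajectories change, which is naturally a group-by-time question. Under a group-by-time contrast the dilution is zero, and what remains is precision.

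That reply stands as far as it goes. A reader might infer that the Fitbit effect is in fact diluted by a third and that much of the power is lost. The documents do not support this: it requires both that baseline is an outcome row and that one group main effect is the reported result, and the second is nowhere stated. Nor can a power loss be derived from the documents, since d and rho are assumed. Setting 64% against 98% compares the least favourable reading with the most efficient alternative; the middle figure of 90% belongs beside them.

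A reader might also infer that a mean-based Fitbit model conflicts with the statement that activity minutes were skewed and could not be transformed. That statement is in the preceding paragraph, which specifies the PAR and accelerometer models. The Fitbit distribution is not described, so no such conflict is shown.

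The reply does not settle the matter. The trajectory aim concerns daily data, whereas the analysis section restricts itself to the measurement weeks and speaks of group differences. On either reading the coefficient to be reported is unspecified, and the baseline week could be used more efficiently.

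**Conclusion.** The point holds in conditional form. The Fitbit weeks appear to include the pre-randomisation week, and the stated model has no visit term, group-by-visit term or baseline adjustment. There are two cases:
- **The group term is the result.** The estimate is two thirds of the effect. This needs complete data and equal effects at 6 and 12 months but no assumption about rho. It is smaller if follow-up weeks are missing or if the effect fades.
- **A group-by-visit contrast with free baseline is the result.** There is no dilution, but the 6-month contrast carries 18% to 54% more variance than a baseline-adjusted one for rho from 0.7 down to 0.3.

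The variance and power figures are illustrations under equal variances and a common correlation. The consequence is limited to a secondary outcome. The primary ActiGraph analysis adjusts for baseline, and nothing here touches it. The change should be made because it improves the analysis on either reading at almost no cost.

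**What to change.** Replace the model sentence with one that states the outcome rows, the fixed effects and the contrasts:
- Outcome: weekly Fitbit minutes at 6 and 12 months only.
- Terms: baseline-week Fitbit minutes, group, visit and group-by-visit, with the subject intercept kept and clustering by yoked group.
- Results: the 6-month group contrast first, then the 12-month contrast.

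A constrained-baseline model is an alternative. It keeps the baseline week as an outcome row but sets the arm means equal there. It has the advantage of retaining girls who lack a usable baseline Fitbit week, whom the covariate form would drop.

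The cost is one sentence in the analysis plan and, if the analysis has already been run, a refit on data already collected. If the fitted model already contained a group-by-visit term, saying so and naming the contrast removes the question of dilution; the gain in precision from using baseline this way would still be available.
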